Study Design	
Multi-center, open-label, randomized, controlled trial with 2 cohorts:
 
 1. Maintenance CNI based immunosuppression therapy 2. polyTregs 
The original study design included a third treatment arm (donor alloantigen reactive Tregs or darTregs). One subject was treated with darTregs prior to protocol version 9.0 in which this treatment arm was eliminated due to excessive manufacturing failures.

Primary Safety Endpoints	
The safety of polyTregs (Group 2) will be described in comparison with CNI-based maintenance IS therapy (Group 1) by:
 
 1. The timing and incidence of Banff 2A or higher acute cell-mediated rejection and/or acute antibody mediated rejection 2. The timing and incidence of study defined Grade 3 or higher infection
Secondary Safety Endpoints for polyTregs	
The safety of PolyTregs will also be described in Groups 1 and 2 by:
 
 1. Timing, incidence, and severity of polyTreg infusion reactions 2. Timing, incidence, and severity of culture-proven and clinically diagnosed infections after polyTreg infusion 3. Timing, incidence, and severity of acute rejection using Banff grading 4. Timing and incidence of BK viremia and CMV reactivation 5. Timing and incidence of > 10% decrease in eGFR compared to baseline
Secondary Safety Endpoint for mTOR Therapy	
The safety of mTOR therapy after Treg infusion will be assessed by the incidence and timing of acute rejection. Subjects who receive Tregs and convert to mTOR therapy will be compared to subjects who did not convert to mTOR therapy, as well as subjects in Group 1.

Primary Efficacy Endpoint	
The primary efficacy endpoint will be the change in inflammation as measured by the percentage area of cortex occupied by inflammatory cells using computer-assisted quantitative image analysis on the biopsy 7 months after group allocation, expressed as the percent change relative to the baseline biopsy.

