3.3.2 Secondary Safety Endpoint for mTOR Therapy

The safety of mTOR therapy after Treg infusion will be assessed by the timing and incidence of acute rejection in Group 2. Subjects who receive Tregs and convert to mTOR therapy will be compared to subjects who did not convert to mTOR therapy; as well as subjects in group 1.

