15.3.2. Endpoint Assessments

15.3.2.1 Primary and Secondary Safety Endpoints

Table 7. Analyses of Safety Endpoints describes the safety endpoints and their corresponding parameters to be estimated in the study. Safety endpoints will be listed or summarized, as appropriate, using standard descriptive statistics for continuous and categorical data.

Table 7. Analyses of Safety Endpoints

ENDPOINT	DESCRIPTIVE PARAMETER	ANALYSIS POPULATION
Primary Endpoint		
Incidence of severe acute rejection or antibody mediated rejection in subjects receiving polyTregs in comparison with CNI-based maintenance IS therapy.	Proportion with exact binomial 95% confidence limits	miITT1
Incidence of severe infection in subjects receiving polyTregs in comparison with CNI-based maintenance IS therapy.	Proportion with exact binomial 95% confidence limits	miITT1
Secondary Endpoints – Treg safety		
Incidence of polyTregs infusion reactions (episodes of fever, bronchospasm, hypoxia, cytokine release syndrome, or infusion site reaction)	Proportion with exact binomial 95% confidence limits	miITT2
Severity of polyTregs infusion reactions	Descriptive CTCAE categories	miITT2
Incidence of culture-proven and clinically diagnosed infections	Proportion with exact binomial 95% confidence limits	miITT1
Severity of culture-proven and clinically diagnosed infections	Descriptive CTCAE categories	miITT2
Incidence of severe infection in subjects receiving polyTregs in comparison with CNI-based maintenance IS therapy.	Proportion with exact binomial 95% confidence limits	miITT1
Timing of acute rejection	Mean time to rejection and standard deviation	miITT1
Incidence of acute rejection	Proportion with exact binomial 95% confidence limits	miITT1
Severity of acute rejection	Descriptive Banff criteria	miITT1
Incidence of CMV reactivation	Proportion with exact binomial 95% confidence limits	miITT1
Incidence of BK viremia	Proportion with exact binomial 95% confidence limits	miITT1
Incidence of >10% decrease in eGFR from baseline	Proportion with exact binomial 95% confidence limits	miITT1
Secondary Endpoints – mTOR therapy		
Incidence of acute rejection	Proportion with exact binomial 95% confidence limits	miITT2 (Treg mTOR vs Treg no mTOR)

15.3.2.2 *Supportive Analyses of the Primary Safety Endpoints*

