Secondary Endpoint(s)	
Secondary Endpoints for polyTregs – Clinical
 
 
1. Proportion of participants exhibiting a relative decrease of 25% or more inflammation between the baseline kidney biopsy and the biopsy 2 weeks after polyTregs, measured as the percentage area of cortex occupied by inflammatory cells using computer-assisted quantitative image analysis.
 
2. Number of participants who exhibit a relative decrease of 50% or more inflammation on kidney biopsy at 2 weeks after polyTregs
 
3. Timing, incidence, and severity of polyTreg infusion reactions
 
4. Timing, incidence, and severity of culture-proven and clinically diagnosed infections after polyTreg infusion
 
5. Timing, incidence, and severity of acute rejection using Banff grading
 
6. Timing and incidence of BK viremia and cytomegalovirus (CMV) reactivation
 
7. Timing and incidence of >10% decrease in eGFR compared to baseline
 
 
Secondary Endpoints for mTOR Therapy – Clinical
 
 
1. Incidence and timing of acute rejection, comparing participants who receive Tregs and convert to mTOR therapy to subjects who do not convert to mTOR therapy and participants in Group 1.
 
 
Secondary Endpoints – Mechanistic
 
 
1. Persistence of infused Tregs in blood and biopsies using deuterium labeling and T-cell repertoire analysis (Group 2)
 
2. Cytokine and CRM mRNA and protein profiles in the urine as correlates of acute rejection and/or histologic evidence of inflammation and graft fibrosis (Groups 1 and 2)
 
3. Peripheral blood kSORT (kidney solid organ response test) mRNA expression of rejection/increased immune response (Groups 1 and 2)
 

Accrual Objective	14 participants total: 7 participants on CNI maintenance therapy 7 participants to receive polyTregs
Study Duration	6.5 Year Accrual, 12 Months Follow Up

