#### 4. ANALYSIS SAMPLES

**Modified Intent-to-Treat Sample 1 (mITT1)** – The mITT1 sample consists of all subjects allocated to the CNI-based treatment regimen or received polyTregs while on study.

**Modified intent-to-Treat Sample 2 (mITT2)** – The mITT2 sample consists of all subjects who received polyTregs (Group 2).

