## **8.2. Secondary Endpoints**

All secondary endpoint analyses will use the mITT1 population, unless otherwise specified.

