### **8.2.1. Endpoints**

**Variable:** Secondary incidence endpoints including:

Endpoint	Time Frame
polyTreg infusion reactions	405 days post-group allocation
Culture-proven and clinically diagnosed infections	405 days post-group allocation

Acute rejection using Banff grading	405 days post-group allocation
BK viremia after polyTregs infusion	405 days post-group allocation
CMV reactivation after polyTregs infusion	405 days post-group allocation
>10% decrease in eGFR compared to baseline	405 days post-group allocation
Acute rejection after converting to mTOR therapy after polyTregs infusion	69 days post-group allocation to 405 days post-group allocation
Proportion of participants exhibiting $\geq 25\%$ decrease of inflammation between baseline kidney biopsy and the week 2 kidney biopsy	Baseline biopsy to Week 2 kidney biopsy
Proportion of participants exhibiting $\geq 50\%$ decrease of inflammation between baseline kidney biopsy and the week 2 kidney biopsy	Baseline biopsy to Week 2 kidney biopsy
Proportion of participants exhibiting $\geq 25\%$ decrease of inflammation between baseline kidney biopsy and the month 6 kidney biopsy	Baseline biopsy to 6 month kidney biopsy (for polyTregs infusion group). Baseline biopsy to 7 months post-group allocation (for maintenance therapy group).

**Analysis:** For each of the above incidence endpoints, the proportion of participants with events will be reported by treatment group and compared using Fisher's Exact test or a Cochran-Mantel-Haenszel test.

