**Population-level summary:**

- **polyTreg infusion reactions - mITT2**
- **Acute rejection using Banff grading** – mITT1, subset to participants that have available Banff lab data
- **Acute rejection after converting to mTOR therapy after polyTregs infusion** - mITT2
- **Proportion of participants exhibiting  $\geq 25\%$  decrease of inflammation between baseline kidney biopsy and the week 2 kidney biopsy** – mITT1, subset to participants with available LCA data from week 2 visit
- **Proportion of participants exhibiting  $\geq 50\%$  decrease of inflammation between baseline kidney biopsy and the week 2 kidney biopsy** – mITT1, subset to participants with available LCA data from week 2 visit
- **Proportion of participants exhibiting  $\geq 25\%$  decrease of inflammation between baseline kidney biopsy and the month 6 kidney biopsy** – mITT1, subset to participants with available LCA data from 6 month visit
- All other endpoints will use the mITT1 sample

**Variable:** Secondary timing endpoints including:

Endpoint	Time Frame
polyTreg infusion reactions	405 days post-group allocation
Culture-proven and clinically diagnosed infections	405 days post-group allocation
Acute rejection using Banff grading	405 days post-group allocation
BK viremia after polyTregs infusion	405 days post-group allocation
CMV reactivation after polyTregs infusion	405 days post-group allocation
>10% decrease in eGFR compared to baseline	405 days post-group allocation
Acute rejection after converting to mTOR therapy after polyTregs infusion	69 days post-group allocation to 405 days post-group allocation

**Analysis:** For each of the above timing endpoints, the mean or median time of event (study days since start of treatment) will be reported by treatment group and compared using ANOVA or the Kruskal-Wallis test (or t-test for comparison of Groups 1 and 2).

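### The mTOR-conversion rejection endpoint is assigned to a sample with no Group 1 subjects, so the promised Group 1 comparison cannot be made; its fixed day 69–405 window may also miss early days on everolimus

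*SAP*

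**What the plan says.** **Comparators promised.** Protocol 3.3.2 says that Treg recipients who convert "will be compared to subjects who did not convert to mTOR therapy; as well as subjects in group 1". The protocol synopsis says the same. The SAP's protocol summary (Section 3) repeats it: "comparing participants who receive Tregs and convert to mTOR therapy to subjects who do not convert to mTOR therapy and participants in Group 1".

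**Sample assigned.** SAP 8.2 sets a default: "All secondary endpoint analyses will use the mITT1 population, unless otherwise specified". The population lists in 8.2.1 then specify otherwise. Under both the incidence and the timing endpoints, "Acute rejection after converting to mTOR therapy after polyTregs infusion" is given mITT2. SAP Section 4 defines that sample: "The mITT2 sample consists of all subjects who received polyTregs (Group 2". Protocol Table 7 (15.3.2.1) has the same assignment, with a two-way contrast: "miITT2 (Treg mTOR vs Treg no mTOR".

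**Time frame.** SAP 8.2.1 gives this endpoint "69 days post-group allocation to 405 days post-group allocation". SAP 7.1.2 adds a general statement that data will normally enter the analyses whenever they were assessed.

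**Timing of conversion.** Under Protocol 6.1.3, everolimus starts within two weeks after the 2-week post-infusion biopsy. Protocol 10.6 allows infusion up to day 62 after central pathology confirmation, and the note to Appendix 4 says that infusion is no longer tied to the allocation day.

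**The concern.** The safety of changing from a CNI to an mTOR inhibitor is the secondary safety objective (Protocol 1.3), and acute rejection is the only endpoint named for it. An analyst who follows SAP 8.2.1 will restrict the data to polyTreg recipients and then be told to compare treatment groups, of which only one is left. The split that could be made within mITT2, converters against non-converters, is not written into 8.2.1. The split that the summary also promises, converters against Group 1, is not possible in that sample.

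The time frame raises a second, conditional question. Days 69 and 405 are Group 1 visit days counted from allocation, whereas conversion is an individual event counted from infusion and biopsy. If the window is applied literally, a rejection early in the tacrolimus reduction could fall outside the endpoint meant to describe rejection after conversion.

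**Working it through.** **1. Sample against promise.**
- Needed: converters, non-converters and Group 1. With *c* converters, the planned numbers are *c*, 7 − *c* and 7, which total 14.
- Available in mITT2: *c* and 7 − *c*. Group 1 subjects: 0 of 7.
- The mITT1 default in SAP 8.2 does not help, because it yields to any specified sample and mITT2 is specified.
- SAP Section 10 lists several population changes. Loss of the Group 1 comparison is not among them.

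**2. Where days 69 and 405 come from.** In Protocol 10.6, each Group 1 visit day minus its Group 2 counterpart is 41: 48 − 7, 55 − 14, 69 − 28, 125 − 84, 223 − 182, 405 − 364. Hence:
- 69 = 41 (nominal infusion) + 14 (biopsy) + 14 (latest everolimus start)
- 405 = 41 + 364 (last visit)

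Day 69 is therefore the latest nominal first dose for a day-41 infusion, not the earliest.

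**3. On-everolimus days before the window opens, read literally.** Days left out = max(0, 69 − (infusion day + 14 + lag)), where lag is the days from biopsy to first dose, 0 to 14. Tacrolimus is halved for 4 weeks, which gives 28 overlap days.

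| Infusion, day after allocation | First dose at lag 0 / 7 / 14 | Days left out | Share of 28 | Last visit |
|---|---|---|---|---|
| 34 (assumed) | 48 / 55 / 62 | 21 / 14 / 7 | 75 / 50 / 25% | 398 |
| 41 (nominal) | 55 / 62 / 69 | 14 / 7 / 0 | 50 / 25 / 0% | 405 |
| 48 (Appendix 4) | 62 / 69 / 76 | 7 / 0 / 0 | 25 / 0 / 0% | 412 |
| 55 (assumed) | 69 / 76 / 83 | 0 / 0 / 0 | 0% | 419 |

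Day 48 is also the last permitted day if randomization comes 14 days after confirmation (62 − 14). A biopsy 3 days early, as its visit window allows, raises the maxima to 17 days (day 41) and 10 days (day 48). At the other end, infusion after day 41 puts the last visit beyond day 405, by 7 days for a day-48 infusion (412 − 405).

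**4. What one uncounted event would do** (exact binomial 95% limits; the number converting is an assumption):
- All 7 convert: 1/7 = 14.3% (0.4–57.9%) becomes 0/7 (0–41.0%).
- 3 convert: 1/3 = 33.3% (0.8–90.6%) becomes 0/3 (0–70.8%).

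**5. Clock for timing.** SAP 8.2.1 counts event times from the start of treatment without saying what that is here. This is a missing detail rather than an error. With infusion on day 41 and first dose on day 62, a rejection on day 90 is 49 days from infusion (90 − 41) or 28 from first dose (90 − 62).

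**The case against.** **The SAP only carries over Table 7.** This is correct: the conflict starts inside the protocol, between 3.3.2 and Table 7. That locates the error but does not remove it, because the SAP's own summary still promises the Group 1 comparison.

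**Group 1 rejection is reported anyway.** This stands. The overall Banff endpoint covers mITT1 subjects with Banff data. A reader might infer that Group 1 rejection, or early rejections in converters, vanish from the report; the documents do not support that. Rejections are reportable within 24 hours (Protocol 14.2.4) and all adverse events are listed (SAP 9.3). What is missing is a display that sets converters beside Group 1.

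**SAP 7.1.2 brings the data back.** It may, and at both ends of the window, since the sentence does not distinguish them. But it is a hedged general statement under visit windows, and it conflicts with an explicit time frame for this endpoint. Neither text is said to prevail.

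**The 14-day loss is extreme.** It is a ceiling for a day-41 infusion with the biopsy on day 14. It needs everolimus on the biopsy day, although resolution must first be confirmed centrally. With the Appendix 4 infusion day the loss is at most 7 days and may be zero.

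**Day 69 could be a deliberate landmark.** It is the latest nominal start and matches Group 1 Visit 3. That would be a defensible design, but the SAP does not say so, and infusion days are not tied to allocation.

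**Conclusion.** The comparator part is wrong as written. Following SAP 8.2.1 omits a comparison that the protocol synopsis, Protocol 3.3.2 and the SAP summary all promise for the secondary safety objective: 0 of 7 planned Group 1 subjects are in the assigned sample. This needs no assumption beyond the documents' own definitions.

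The time-frame part is conditional. Read literally, the window leaves out 0–14 on-everolimus days for a day-41 infusion and 0–7 for day 48 (biopsy on day 14), more for earlier infusions and none from day 55 on. Actual infusion and first-dose days are not in the documents, and SAP 7.1.2 may restore the data, so the two passages must be reconciled. It would be tempting to conclude that early post-conversion rejections will be dropped, or that the endpoint is biased in favour of conversion. The documents support neither: they show only that days can be lost, and the direction of any bias is not established.

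The point should be settled before database lock. It affects what is displayed for a key safety question in a very small group, not whether events are captured.

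**What to change.** - **Population.** In SAP 8.2.1, for both incidence and timing, replace mITT2 with mITT1 under the same available-Banff-data rule as the other rejection endpoints, so that Group 1 has one denominator throughout. Show three named groups: converters, non-converters and Group 1.
- **Alignment.** Amend protocol Table 7 to match Protocol 3.3.2, and record the change in SAP Section 10.
- **Converters' time frame.** Replace days 69–405 with actual first everolimus dose to last visit, and report time from first dose.
- **Other groups' time frame.** State one matching start, for example day 28 after infusion for non-converters and Day 69/Visit 3 for Group 1. List individually any rejection between the 2-week biopsy and that start or the first dose. The starts will not coincide for early converters, and the listing ensures that no event is lost between them.
- **Reporting.** Give proportions with exact 95% confidence intervals, labelled descriptive, because conversion is selected on resolved inflammation, cell dose and DSA (Protocol 4.3). Whether the SAP should test secondary endpoints at all is a separate matter.

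**Cost.** A few lines of SAP text, one table alignment and a little programming. Concomitant medications are collected (Appendix 3), but the documents do not say that the first everolimus dose date is recorded; confirm this before lock. The display still cannot separate the effect of conversion from the selection of who converts.

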6.4. Rejection after Initiation of Everolimus

Any subject with biopsy proven or treated rejection after the start of study mandated everolimus will discontinue everolimus and resume tacrolimus. Target tacrolimus trough levels will be 4-11 mcg/L.

7. Other Medications

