10.4. Follow Up Visits

Group 2 participants will have study visits on day 1, 7, 14, 28, 84, 182, and 364 after Treg infusion. Participants in Group 1 will have the same visits in parallel with Group 2 patients, starting 48 days after study group assignment. Please refer to Appendix 2 for Group 1 schedule of events and Appendix 3 for Group 2 schedule of events.

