10.6. Visit Windows

Study visits should take place within the time limits specified below (Table 2). The designated visit windows for each scheduled visit are also indicated on the Schedules of Events.

Table 2. Visit Windows	
Study Visit	Visit Window
Study Eligibility Biopsy	5 months \pm 8 weeks
Study Eligibility/ Study Group Allocation	\leq 2 weeks after qualifying biopsy
Group 1 Only	
Day 41/ Visit T0-G1	\pm 3 days
Day 48/ Visit 1	\pm 5 days
Day 55/ Visit 2	
Day 69/ Visit 3	
Day 125/ Visit 4	
Day 223/ Visit 5	\pm 14 days
Day 405/ Visit 6	
Group 2	
PBMC Collection Visit T-16	Dictated by infusion date and manufacturing timeline.
Treg Infusion Day / Visit T0	Infusion can occur any time up to and including day 62 after central pathology confirmation.
Visit T1 / Day 1	\pm 1 hour (Group 2)
Visit 1 / Day 7	\pm 1 day
Visit 2 / Day 14	\pm 3 days
Visit 3 / Day 28	
Visit 4 / Day 84	
Visit 5 / Day 182	\pm 14 days
Visit 6 / Day 364	\pm 14 days

11. Mechanistic Assays

The goal of the mechanistic studies in this trial is to evaluate the impact of polyTregs on the immunological profiles of kidney transplant recipients. We will accomplish this by determining: 1) impact of Treg infusion on the numbers of circulating and graft-infiltrating Tregs; 2) impact of Treg infusion on the inflammation in the graft; 3) impact of Treg infusion on the peripheral blood biomarkers of rejection and graft injury.

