Appendix 4. Manufacturing Timeline

Central Biopsy Reading	Randomization to occur as soon as eligibility is confirmed, no later than 14 days after central biopsy confirmation.		Group 2 Recipient Draw*	Group 2 PolyTreg Infusion																																																											
Randomization Day	##	##	34	48																																																											
Post Biopsy Day	0	1	2	3	4	5	6	7	8	9	10	11	12	13	14	15	16	17	18	19	20	21	22	23	24	25	26	27	28	29	30	31	32	33	34	35	36	37	38	39	40	41	42	43	44	45	46	47	48	49	50	51	52	53	54	55	56	57	58	59	60	61	62

*Group 2 recipient draw must occur 16 days (14-16 days for UCSF) prior to infusion date.

Amendment 8: Group 1 SOE will maintain Day 0 as day of study group assignment. Day 0 label was removed from the Group 2 and 3 SOE to avoid confusion. For Group 2 and 3, the day of infusion will no longer be linked to study group assignment but rather to central biopsy reading confirmation.

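### The SAP frames rejection after mTOR conversion by Group 1 visit days (69 to 405), so a converter's first days on everolimus can fall outside it

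*SAP*

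**What the plan says.** SAP 8.2.1 lists acute rejection after conversion to mTOR therapy in its incidence table and again in its timing table. Both give the frame "69 days post-group allocation to 405 days post-group allocation", and both population lines give mITT2, the participants who received polyTregs. The timing analysis reports event times as "study days since start of treatment", which is a different origin from the frame.

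SAP section 3 describes the endpoint as "comparing participants who receive Tregs and convert to mTOR therapy to subjects who do not convert to mTOR therapy and participants in Group 1". Protocol 3.3.2 agrees: converters "will be compared to subjects who did not convert to mTOR therapy; as well as subjects in group 1". Protocol Table 7, however, gives only the Treg groups with and without mTOR, in mITT2. Neither protocol 3.3.2 nor Table 7 sets a calendar window, and SAP section 10 lists none among its changes.

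On the schedule, protocol 10.4 says "Group 2 participants will have study visits on day 1, 7, 14, 28, 84, 182, and 364 after Treg infusion". Protocol Table 2 says "Infusion can occur any time up to and including day 62 after central pathology confirmation", and the amendment note under Appendix 4 says that "the day of infusion will no longer be linked to study group assignment but rather to central biopsy reading confirmation". Under protocol 6.1.3, everolimus begins no more than 2 weeks after the post-infusion biopsy that shows resolution.

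**The concern.** The frame is written on a clock that does not govern the people who convert. Days 69 and 405 after allocation are Group 1 visits. A Group 2 participant reaches the matching visits on those days only if infused on day 41.

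The days at risk of being missed are the first ones on everolimus with tacrolimus halved. Protocol 6.4 says: "Any subject with biopsy proven or treated rejection after the start of study mandated everolimus will discontinue everolimus and resume tacrolimus". A participant who rejected in that interval, before day 69, would have left everolimus yet would still be tabulated as a converter without an event. This endpoint is the only planned comparison of rejection by conversion status, so no other table would show it in that form.

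**Working it through.** **Where days 69 and 405 come from.** Subtract each Group 2 post-infusion visit day from the matching Group 1 day in protocol Table 2: 41−0, 48−7, 55−14, 69−28, 125−84, 223−182, 405−364. The difference is 41 every time. So 69 = 41+28 (Visit 3) and 405 = 41+364 (Visit 6). The frame fits Group 2 only if infusion is on day 41 after allocation. No document states that infusion day; it is inferred from this offset.

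**Inputs and formulas.** Let I be the infusion day counted from allocation.
- Biopsy day = I+14 (protocol 8.3).
- Everolimus start = I+14 to I+28 (protocol 6.1.3).
- Days on everolimus before the frame opens = max(0, 69 − start day).
- Visit 6 = I+364. Days after the frame closes = max(0, I+364−405).

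| I | Biopsy | Everolimus start | Days missed at front | Visit 6 | Days cut at end |
|---|---|---|---|---|---|
| 34 | 48 | 48–62 | 7–21 | 398 | 0 |
| 41 | 55 | 55–69 | 0–14 | 405 | 0 |
| 48 | 62 | 62–76 | 0–7 | 412 | 7 |
| 62 | 76 | 76–90 | 0 | 426 | 21 |

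**Status of each row.** Day 41 is the inferred nominal case. The Appendix 4 table is broken in the text, but as it reads it may place infusion on randomization day 48. That is also the latest infusion if allocation comes 14 days after central confirmation (62−14). Day 62 is the latest if allocation is on the day of confirmation. Day 34 is an assumed earlier infusion, shown for range. Moving the biopsy to day 11, within its ±3-day window, makes the earliest start with I=41 day 52, and 69−52 = 17 days.

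**Non-converters.** The same frame applies to them. From the 2-week biopsy to day 69 is 69−55 = 14 days when I=41, and 69−62 = 7 days when I=48. Rejections in those days are excluded for them as well.

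**Effect of one uncounted event among converters** (exact binomial limits; the numbers of converters are assumed):
- 7 converters: 1/7 = 14.3% (0.4–57.9%) becomes 0/7 (0–41.0%).
- 3 converters: 1/3 = 33.3% (0.8–90.6%) becomes 0/3 (0–70.8%).

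**The case against.** The strongest reply is that a time-frame column gives nominal follow-up, not an exclusion rule. Infusion reactions carry a 405-day frame, which plainly describes follow-up rather than risk. SAP 7.1.2 says that data are in general analysed whatever the time of assessment, and the endpoint's own name already sets the start at conversion. This has weight, but the 7.1.2 sentence is a general one and does not clearly override a specific frame given twice. The SAP should say which applies.

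A second reply is that day 69 is a landmark: 41+14+14 is the last nominal day on which everolimus can start, and a common late start avoids crediting converters with event-free time. That is a reasonable design, but the SAP does not state it or say how a converter who rejects before day 69 is handled. A fixed allocation day is also a poor landmark when infusion day varies.

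Several objections stand. Fourteen days is a ceiling: it needs everolimus on the day of the biopsy, although the central pathologist must first confirm resolution. The mITT2 restriction follows protocol Table 7, so the conflict over Group 1 lies within the protocol (3.3.2 against Table 7). A reader might also infer that the frame biases the comparison in favour of conversion. The documents do not support that, because early rejections in Treg non-converters, who may have unresolved inflammation, are dropped by the same rule and the net direction is unknown.

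**Conclusion.** The point holds as a minor defect in one descriptive secondary safety comparison. Applied as written, the frame omits 0 to at most 14 days after the first everolimus dose with infusion on day 41 and a day-14 biopsy. With infusion on day 48 it omits 0 to 7 days at the front and 7 days at the end. The exact loss depends on each participant's infusion and start dates, which the documents do not fix. About 7 participants at most can convert.

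A reader might conclude that early rejections would disappear from the report. They would not: the general acute-rejection endpoint in SAP 8.2.1 covers 405 days from allocation, and SAP 9.3 provides a listing of all adverse events. What is lost is their attribution to conversion status. Nor does the point touch the primary safety or efficacy analyses.

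**What to change.** In both SAP 8.2.1 tables, replace the day 69–405 frame for this endpoint:
- Converters: first everolimus dose to Visit 6 (Day 364 after infusion).
- Treg non-converters: 2-week biopsy to Visit 6, using day 14 after infusion if no biopsy was done.
- Count event time from the same start dates.

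List every rejection after the 2-week biopsy with days since infusion and, where it applies, since first everolimus dose. State that converters are event-free by definition between biopsy and first dose, up to about 14 days. The unequal starts create this gap, and a rejection in it would probably stop conversion and so fall among the non-converters. The listing discloses the gap but does not remove it.

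Because protocol 3.3.2 and SAP section 3 name Group 1 while Table 7 does not, also report Group 1 descriptively from day 55 (Visit 2) to Visit 6. Record these changes in SAP section 10.

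Follow-up stays close to equal with a day-14 biopsy: converters 364−28 to 364−14 = 336–350 days, non-converters 364−14 = 350, Group 1 405−55 = 350. The cost is a few lines of SAP text and one short listing, using infusion, biopsy and everolimus start dates.
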